5.1 Number of Subjects

It is planned to enroll 16 subjects for participation in this study. [REDACTED]

[REDACTED]

5.2 Inclusion Criteria

Subjects must meet all of the following criteria to be included in the study:

1. Male or female, light smoker (no more than 10 cigarettes daily) or non-smoker, ≥ 18 and ≤ 50 years of age, with body mass index (BMI) ≥ 18.5 and $\leq 30.0 \text{ kg/m}^2$ and body weight $\geq 50.0 \text{ kg}$ for males and $\geq 45.0 \text{ kg}$ for females.
2. Healthy as defined by:
 - a. the absence of clinically significant illness and surgery within 30 days prior to dosing.
 - b. the absence of clinically significant history of neurological, endocrine, cardiovascular, respiratory, hematological, immunological, psychiatric, gastrointestinal, renal, hepatic, and metabolic disease.
3. Female subjects of non-childbearing potential must be:
 - a. post-menopausal (no menstrual period at least 12 consecutive months without any other medical cause and FSH and LH values consistent with being menopausal); or
 - b. surgically sterile (bilateral oophorectomy, bilateral salpingectomy, hysterectomy or tubal ligation) at least 3 months prior to dosing.
4. Sexually active female subjects of childbearing potential must be willing to use an acceptable contraceptive method throughout the study as detailed in section 7.1.
5. Willing to take off dentures or mouth piercing at the time of dosing.

6. Able to understand the study procedures and provide signed informed consent to participate in the study.

5.3 Exclusion Criteria

Subjects to whom any of the following applies will be excluded from the study:

1. Any clinically significant abnormal finding at physical examination.
2. Clinically significant abnormal laboratory test results (may be repeated up to two times) or positive serology test results for hepatitis B surface antigen (HBsAg), hepatitis C virus (HCV) antibody, or human immunodeficiency virus (HIV)-1 and HIV-2 antibodies at screening.
3. Positive pregnancy test or lactating female subject.
4. Positive urine drug screen.
5. Known allergic reactions to sapropterin dihydrochloride or other related drugs, or to any excipient in the formulation.
6. Clinically significant ECG abnormalities or vital signs abnormalities (systolic blood pressure lower than 90 or over 150 mmHg, diastolic blood pressure lower than 50 or over 90 mmHg, or pulse rate less than 50 or over 100 bpm) at screening. ECG and vital signs may be repeated up to two times, to determine if the values are significantly abnormal.
7. Recreational use of soft drugs (such as marijuana) within 1 month or hard drugs (such as cocaine, phencyclidine [PCP], crack, opioid derivatives including heroin, and amphetamine derivatives) within 3 months prior to screening.
8. History of alcohol addiction requiring treatment.
9. History of abuse of medicinal product or drugs within the last 3 years.
10. History or presence of alcoholism within the last 3 years. (>40 g ethanol/day or more than 10 units per week [1 unit = 150 mL of wine, or 360 mL of beer, or 45 mL of 45% alcohol]).
11. Use of medications within the timeframes specified in section 7.2.
12. Participation in a clinical research study involving the administration of an investigational or marketed drug or device within 30 days prior to dosing, administration of a biological product in the context of a clinical research study within 90 days prior to dosing, or concomitant participation in an investigational study involving no drug or device administration.
13. Known predisposition to seizures.
14. Donation of plasma within 7 days prior to dosing or donation or loss of 500 mL or more of whole blood within 8 weeks prior to dosing.
15. Presence of orthodontic braces or orthodontic retention wires, or any physical findings in the mouth or tongue that would be likely to interfere with successful completion of the dosing procedure.

16. Females who:

- a. Have discontinued or changed the use of implanted, intrauterine, intravaginal, or injected hormonal contraceptives within 6 months prior to study treatment administration.
- b. Have discontinued or changed the use of oral or patch hormonal contraceptives within 1 month prior to study treatment administration.

17. Any reason which, in the opinion of the Investigator, would prevent the subject from participating in the study.

5.4 Subject Withdrawal and Replacement

Subjects will be advised that they are free to withdraw from the study at any time. Over the course of the study, the Sponsor and the Investigator or designee may withdraw any subject from the study for one of the reasons described below; subject withdrawal will be done in accordance with the clinical site's SOP:

- Safety reason;
- Non-compliance with protocol requirements;
- Significant protocol deviation;
- Positive pregnancy test, drug screen, or alcohol breath test.

Subjects who experience vomiting within 10 hours after study treatment administration will be removed from that period of the study. Their continued participation in the study will be evaluated by the Investigator and PK Scientists prior to the next study treatment administration.

Subjects who experience vomiting after this time will be assessed for their continued participation in the study by the Investigator.

Subjects excluded from dosing in one period as per criteria listed above, may be invited to participate in subsequent periods of the study if deemed appropriate by the Investigator and appropriate from a statistical standpoint (i.e., would permit adequate statistical comparison). However, subjects with positive pregnancy test, drug screen, or alcohol breath test will be definitively withdrawn from the study.

Subjects who withdraw prior to the first dosing may be replaced with a standby subject. Subjects who withdraw or are withdrawn from the study after the first dosing will not be replaced.

Subjects who withdraw or are withdrawn will be asked to remain at the clinic until the Investigator or designee agrees that the subject is fine and can be discharged. As soon as subject withdrawal is confirmed, blood sampling will be stopped. A PK blood sample may be collected at the time of withdrawal if deemed required by the Investigator. EOS/early termination (ET) procedures will be performed at the time of withdrawal from the study or as soon as possible thereafter.

5.4.1 Use of Data for Discontinued Subjects

Data that was obtained prior to a subject's discontinuation in this study will be maintained, used, and included in subsequent analyses, as applicable. If a subject withdraws from the study, the subject may request the destruction of samples.

No analyses will be performed on the samples outside of the protocol requirements without the subject's consent.

6. Study Treatments

6.1 Study Treatment Supplies and Accountability

It is the responsibility of the Sponsor to ensure that study treatments provided for this study are manufactured under Good Manufacturing Practice (GMP) and are suitable for human use. The reference product will be obtained from [REDACTED]. The Sponsor is responsible to ship a sufficient amount of dosage units to allow the clinical site to maintain an appropriate sampling for the study.

The study treatments will be stored at the clinical site pharmacy as per applicable requirements in a locked, environmentally-controlled medication room with restricted access. Container(s) will be labeled according to applicable regulations.

Individual doses for each subject and period will be dispensed at the clinical site pharmacy, as per appropriate SOP, according to the randomization scheme, and according to the subject's weight measured at Period 1 check-in, in appropriate syringes/containers indicated with at least the project number, the period number and the subject number/spare number. Please refer to the pharmacy and dosing plans for detailed procedures on dispensing.

All study treatments received at the site will be inventoried and accounted for throughout the study and the result recorded in the study treatment accountability record according to the clinical site appropriate SOP.

At the completion of the study, unused study treatment(s) will be retained at the clinical site, returned to the Sponsor, or destroyed, as requested by the Sponsor. No study treatment(s) will be destroyed without written permission from the Sponsor.

6.2 Investigational Products

Test: Sapropterin dihydrochloride 100 mg/mL oral suspension (product code: RLF-OD032) (APR Applied Pharma Research s.a., Switzerland)

Reference: Kuvan (sapropterin dihydrochloride) 100 mg powder for oral solution [REDACTED]

[figure not shown]
6.3 Identification of Treatments

Treatment A: 1 x 10 mg/kg dose* of sapropterin dihydrochloride oral suspension 100 mg/mL administered without water under fasting conditions.

Treatment B: 1 x 10 mg/kg dose* of sapropterin dihydrochloride oral suspension 100 mg/mL administered without water under fed conditions.

Treatment C: 1 x 10 mg/kg dose* of sapropterin dihydrochloride oral suspension 100 mg/mL administered with water under fed conditions.

Treatment D 1 x 10 mg/kg dose* of Kuvan (sapropterin dihydrochloride) 100 mg powder for oral solution dissolved in water and administered under fed conditions.

6.4 Randomization and Blinding

This study will be an open-label study due to the objective nature of the data. Subjects will be administered each treatment according to the block randomization scheme. A 4-sequence Williams design will be used (e.g.: ADBC, BACD, CBDA and DCAB):

Table 3. Treatment Sequence

Sequence	Treatment			
	Period 1	Period 2	Period 3	Period 4
DCAB	D	C	A	B
ADBC	A	D	B	C
BACD	B	A	C	D
CBDA	C	B	D	A

Subjects will be assigned consecutive subject numbers in an ascending order. Each number will identify a subject and determine the sequence of study treatment administration according to the randomization scheme.

The randomization code will not be available to the bioanalytical facility until the clinical and analytical phases of the study have been completed.

6.5 Study Treatment Administration

Subjects will be asked to take off dentures or mouth piercing at the time of dosing. A mouth check will be performed to ensure study treatment and fluid (when applicable) consumption. The time of dosing will be set as the time the oral suspension or solution begins to be swallowed. For

[REDACTED]

Treatments A and B: t [REDACTED]

[REDACTED]

Treatment C: t [REDACTED]

[REDACTED]

For Treatment D, the powder for oral solution will be dissolved in 120 mL (± 3 mL) of water within 15 minutes before administration and the solution will be swallowed at the time of study treatment administration. The powder should be placed in water and stirred until dissolved. The powder should dissolve completely.^{1,2} To ensure that the entire dose is consumed, the dosing cup will be rinsed twice with an additional 60 mL (± 1 mL) of water each time (total volume of 120 mL (± 2 mL)) and the contents will be swallowed. No additional water will be given to the subjects.

6.6 Administration of Food and Fluid

For Treatment A:

Subjects will fast from at least 10 hours prior to study treatment administration until at least 4 hours post-dose.

For Treatment B, C, and D:

After an overnight fast of at least 10 hours, subjects will consume a high-fat, high-calorie breakfast starting 30 minutes prior to study treatment administration.

Table 4. High-Fat, High-Calorie Breakfast

	Calories (kcal)	Total Fat (g)	Carbohydrates (g)	Protein (g)
2 eggs	140	10	0	12
10 g of butter for cooking eggs	70	8	0	0
2 slices of whole wheat toast (approximately 64 g)	160	2	31	7
10 g of butter for toast	70	8	0	0

3 triangle pieces of hash brown potatoes (approximately 130 g)	218	14	23	2
250 mL of whole milk	160	8	12	8
3 strips of chicken bacon (approximately 63 g)	105	7	0	9
Total weight (g)		57	66	38
Total calories (kcal)	923	514	262	152
Relative caloric content		56%	28%	16%

Note: Due to supply chain issues, some ingredients may not be available therefore, the content of the high-fat, high-calorie breakfast is subject to change. Any change will be notified to the Sponsor and ensured that the total caloric content and breakdown between fat, carbohydrate, and protein is maintained according to FDA requirements: high-fat (approximately 50 percent of total caloric content of the meal) and high-calorie (approximately 800 to 1000 calories). The meal should derive approximately 150, 250, and 500-600 calories from protein, carbohydrate, and fat, respectively.⁷

Subjects who do not consume the entire meal in the required time will be dismissed from that period of the study prior to study treatment administration. Their continued participation in the remainder of the study will be determined by the Investigator or designate.

Subjects will fast for at least 4 hours post-dose.

For all Treatments:

Standardized meals will be provided throughout confinement (e.g., at 4 hours for lunch, 9 hours for dinner and 13.5 hours for snacks). The meals will be identical for all periods.

Water will be restricted from one hour prior to study treatment administration until one hour post-dose (except the water administered with the study treatment in Treatment C and D). Access to water will otherwise be freely available to subjects.

7. Study Restrictions

Adherence to the restrictions will be confirmed and recorded at each check-in. Subjects who do not comply with these restrictions will be assessed by the Investigator/PK Scientists regarding their continued participation in the study.

7.1 Contraception

Subjects participating in this study must use an acceptable single- or double-method of contraception as defined below:

- Females: from 21 days prior to first study treatment administration until 28 days after the last PK blood sample in the study

- Males: from the day of first study treatment administration until 28 days after the last PK blood sample in the study

Table 5. Acceptable Effective Methods of Contraception

Single-Method	Double-Method (must use at least two)	
Surgically sterile	Diaphragm with Spermicide	Non-hormonal IUD
Postmenopausal	Cervical cap with Spermicide	Vasectomy
Remain abstinent	Condom with Spermicide	Hormonal contraception
Hormonal contraception includes: Oral contraceptives, intra-vaginal devices, hormonal IUD, injections, transdermals, and implants		

Male subjects will be instructed not to donate sperm from the day of first study treatment administration until at least 28 days after the last PK blood sample in the study.

7.2 Concomitant Medications

Subjects will be required to avoid using medications for the timeframes specified below and throughout the study:

- Depot injection or implant of any drug for 3 months prior to dosing;
- Prescription medications for 14 days prior to dosing;
- Any vaccine, including COVID-19 vaccine, for 14 days prior to dosing;
- Over-the-counter (OTC) medications and natural health products (including herbal remedies such as St. John's wort, homeopathic and traditional medicines, probiotics, food supplements such as vitamins, minerals, amino acids, essential fatty acids, and protein supplements used in sports) for 7 days prior to dosing (with the exception of the occasional use of acetaminophen up to 2 g daily).

No concomitant medications will be allowed during the study, with the exception of hormonal contraceptives, medications required for the medical management of an AE, and medications exempted by the Investigator on a case-by-case basis that are judged unlikely to affect the PK profile of the study treatment or subject safety (e.g., topical drug products without significant systemic absorption).

Medications taken by subjects before the first dose will be documented as prior medications and medications taken by subjects after the first dose through to the last study day will be documented as concomitant medications. Any prior or concomitant medication use, other than the allowed medications stated above, will be reviewed and evaluated on a case-by-case basis by the Investigator and PK Scientists to determine if they affect a subject's eligibility or continued participation in the study, or for potential impact on the study results. In accordance with the prescribing information for Kuvan, subjects taking medications known to inhibit folate metabolism, or levodopa, after being administered sapropterin, will be monitored. Subjects taking medications known to affect nitric oxide-mediated vasorelaxation after being administered sapropterin will be monitored for hypotension.

7.3 Drugs, Nicotine and Alcohol

Subjects will be required to abstain from:

- Soft or hard drugs from screening and throughout the study;
- Any nicotine product (including cigarettes) during confinement. No more than 10 cigarettes per day will be allowed during the washout period. No nicotine products (other than cigarettes) will be allowed during the washout period;
- Alcohol-based products from 48 hours prior to admission until after the last PK blood sample collection of each period.

7.4 Diet

Subjects will be required to abstain from:

- Food or beverages containing grapefruit, Seville orange, starfruit, pomegranate, pineapple, or pomelo from 7 days prior to dosing and throughout the study;
- Food or beverages containing xanthine derivatives or xanthine-related compounds (coffee, black/green tea, chocolate) or energy drinks from 48 hours prior to dosing until after the last PK blood sample collection of each period;
- Food containing poppy seeds from 24 hours prior to admission of each period.
- Chewing gum will be prohibited at all times during the confinement.

7.5 Posture and Physical Activity

Subjects will be required to remain seated and avoid lying down or sleeping for 6 hours after study treatment administration.

Failure of subjects to comply with these requirements does not constitute a deviation from the protocol if it is medically necessary, required for procedures, or to go to the bathroom. When appropriate, subjects will be accompanied by a staff member while walking. Vigorous activity will be prohibited at all times during the confinement.

8. Study Procedures

Subjects must provide written informed consent (privacy, volunteer, and informed consent) prior to initiation of any study procedures.

Unless otherwise specified, study procedures will be conducted in accordance with clinical site SOPs.

Every effort will be made to schedule and perform the procedures as close to the nominal time as possible, giving considerations to appropriate posture conditions, practical restrictions, and other procedures to be performed at the same time point.

PK blood sample collection will be performed closest to the nominal time. When vital signs measurement or ECG recording coincide with a blood collection, they should preferably be performed before the blood collection, whenever possible.

Table 6. Scheduled Windows of Allowance for Vital signs and ECG

Procedure	Timepoint	Acceptable Window from Scheduled time
Vitals	Pre-dose (0-hour)	Within 180 minutes prior to dosing
	>0 hours	±20 minutes
ECG	Pre-dose (0-hour)	From check-in to dosing
	>0 hours	±30 minutes

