Investigational Products:	Test: Sapropterin dihydrochloride 100 mg/mL oral suspension (product code: RLF-OD032) (APR Applied Pharma Research s.a., Switzerland) Reference: Kuvan (sapropterin dihydrochloride) 100 mg powder for oral solution [REDACTED]
Study Phase and Type:	Phase 1 – Comparative Pharmacokinetic (PK), Food-Effect, and Water-Effect
Objectives:	Primary objectives: • [REDACTED] • [REDACTED] Secondary objective: • [REDACTED]
Endpoints:	Primary endpoints: • PK ○ Uncorrected and baseline-corrected sapropterin AUC_{0-t} , $AUC_{0-\infty}$, and C_{max}

	
Secondary endpoints:
 
Study Design:	
This is a single center, Phase 1, randomized, open-label, single-dose, 4-treatment, 4-period, 4-sequence, crossover study designed to compare the PK of sapropterin from the Test and Reference products, and to evaluate the effect of food and the effect of water administration on the bioavailability of sapropterin from the Test product in healthy subjects.
 
In each period, subjects will receive a single 10 mg/kg dose of sapropterin dihydrochloride on Day 1, under fasting or fed conditions, and with or without water, followed by 24 hours of PK sampling.
 
The study will include a screening visit from Day -30 to Day -1. In each period, eligible subjects will be admitted to the clinical site on Day -1 and will be confined until completion of the assessments on Day 2. There will be a washout period of at least 7 days between doses.

Study Population:	
It is planned to enroll 16 healthy adult males and females for participation in this study. All attempts will be made to have an equal number of males and females.

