Day	-30 to -1 (of Period 1)	-1 of Period 1 or prior to Period 1 dosing	-1 of Period 2, 3, 4	1	2 EOS/ET¹³
Screening consent ¹	X				
Informed consent ²		X			
Inclusion/exclusion criteria	X ³	X ⁴			
Demographic data	X ³				
Medical and medication history	X ³	X	X		
Confinement ⁵		X	X	X	
Discharge					X
Study treatment administration					
Sapropterin dihydrochloride oral suspension				X ⁶	
Kuvan powder for oral solution				X ⁶	
Pharmacokinetics					
Blood samples for PK analysis ⁷				X	X
Safety					
Physical examination ⁸		X			X
Body measurements (height, weight, BMI)	X ³	X ⁹			
Vital signs ¹⁰	X ³	X	X	X	X
12-lead ECG ¹¹	X ³			X	X
Serology tests	X ³				
Biochemistry, hematology, and urinalysis tests	X ³				X
FSH/LH (for post- menopausal females)	X ³				
Serum pregnancy tests	X ³	X	X		X
Urine pregnancy test		X	X		
Urine drugs of abuse	X ³	X	X		
Breath alcohol		X	X		
Monitoring and recording of AEs and prior/concomitant medication use		X	X	X	X

Abbreviations: AE = adverse event; BMI = body mass index; ECG = electrocardiogram; EOS = end of study; ET = early termination; FSH = follicle-stimulating hormone; LH = luteinizing hormone; PK = pharmacokinetic.

1 Includes privacy and volunteer consent. During screening, subjects will consent to and sign privacy and volunteer consent forms.

2 An informed consent form (ICF) specific to this study will be signed by all subjects at Period 1 check-in (Day -1), and before any study specific procedure.

- 3 Screening procedures can be done either at the screening visit or at Period 1 check-in (or repeated at both screening visit and Period 1 check-in if deemed necessary by the Investigator).
- 4 Complete outstanding procedures for inclusion/exclusion criteria confirmation.
- 5 Confinement period is at least 10.5 hours pre-dose until 24 hours post-dose.
- 6 On Day 1 of each period, subjects will receive one of the four treatments, according to the randomization scheme.
- 7 A total of 20 blood samples will be collected for PK analysis in each period: -1, -0.5, pre-dose (0-hour), and 0.333, 0.667, 1, 1.5, 2, 2.5, 3, 3.5, 4, 4.5, 5, 5.5, 6, 8, 12, 16, and 24 hours post-dose.
- 8 A complete physical examination will be performed at Period 1 check-in. A brief physical examination will be performed at EOS. Refer to sections 8.1 and 8.4 for more details.
- 9 Weight only at check-in of Period 1.

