- 10 Blood pressure, pulse rate, respiration rate, and temperature will be measured at screening and EOS. Temperature will be measured daily during confinement. Blood pressure and pulse rate will be measured before dosing (0-hour) and at 4 and 6 hours post-dose of each period.
- 11 12-lead ECG will be measured at screening, before dosing (0-hour), at 4 and 6 hours post-dose of each period, and at EOS.
- 12 There are 4 treatment periods. There will be a washout period of at least 7 days between doses.
- 13 EOS evaluations will be performed prior to study discharge of the last period. In case of ET, EOS procedures will be performed as soon as possible.

1. Introduction

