8.2 Test/ Procedures at check-in

Check-in of Period 1

- ICF signature for the study (if not done before);
- Medical and medication history;
- Any outstanding screening procedure that is not completed, or needs to be repeated;
- Complete physical examination including assessments of the following: head, eyes, ears, nose, throat (HEENT), neck, chest, lungs, abdomen, musculoskeletal, dermatological, cardiovascular/peripheral vascular, and general neurological examination;
- Temperature measurement;

- Weight;
- Urine drugs of abuse (amphetamines, barbiturates, benzodiazepines, cannabinoids, cocaine, methadone, opiates, phencyclidine, and tricyclic antidepressants);
- Urine β -HCG and serum β -HCG (females only);
- Breath alcohol;
- Confirm inclusion/exclusion criteria.

Check-in of Period 2, 3, 4

- Temperature measurement;
- Urine drugs of abuse (amphetamines, barbiturates, benzodiazepines, cannabinoids, cocaine, methadone, opiates, phencyclidine, and tricyclic antidepressants);
- Urine β -HCG and serum β -HCG (females only);
- Breath alcohol;
- Medical and medication history.

Clinical study personnel reserve the right to conduct additional testing (e.g., breath alcohol test, diagnostic imaging) at any time throughout the study.

8.3 On-study procedures:

- Temperature measurement daily;
- Vital signs (blood pressure and pulse rate) will be measured after the subjects have been resting for at least 3 minutes in a sitting position: before dosing (0-hour), and at 4 and 6 hours post-dose;
- 12-lead ECG will be recorded after the subjects have been resting in a semi-recumbent or supine position: before dosing (0-hour), at 4 and 6 hours post-dose;
- Study treatment administration; and
- Pharmacokinetic Blood Sample Collection: -1, -0.5, pre-dose (0), and 0.333, 0.667, 1, 1.5, 2, 2.5, 3, 3.5, 4, 4.5, 5, 5.5, 6, 8, 12, 16, and 24 hours post-dose.

Table 8. Time Windows for PK Blood Samples

Day	Time point	Time window
1	-1 hour, and -0.5 hour	± 5 minutes
	Pre-dose (0-hour)	Within 5 minutes
	0.333, 0.667, 1, 1.5, 2, 2.5, 3, 3.5, 4, 4.5, 5, 5.5, and 6 hours	± 1 minute
	8, 12, and 16 hours	± 3 minutes

2	24 hours	±3 minutes
---	----------	------------

Samples collected outside the acceptable window will not be considered as protocol deviations, but rather the actual clock time of each sample collection will be recorded.

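### Table 6 lets the 0-hour ECG be recorded at check-in on the day before dosing, which makes it a poor reference for the post-dose tracings

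*Combined protocol and SAP*

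**What the plan says.** Table 6 (section 8) sets different tolerances for the two pre-dose safety readings. Vital signs at 0 h must be taken "Within 180 minutes prior to dosing". The 0-hour ECG may be taken "From check-in to dosing". Post-dose ECGs have a window of 30 minutes either side, and post-dose vital signs 20 minutes.

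Admission is the day before dosing. The synopsis says "eligible subjects will be admitted to the clinical site on Day -1 and will be confined until completion of the assessments on Day 2", and Table 1, footnote 5, adds "Confinement period is at least 10.5 hours pre-dose until 24 hours post-dose".

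The ECG schedule is in Table 1, footnote 11: "12-lead ECG will be measured at screening, before dosing (0-hour), at 4 and 6 hours post-dose of each period, and at EOS". The ECG row of Table 1 is marked at screening, Day 1 and Day 2, and in neither admission column. The check-in lists in section 8.2 contain no ECG. Section 8.3 lists it among the on-study procedures, before dosing.

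Two restrictions matter for the state of the subject at check-in. Section 6.6 requires a fast of at least 10 h before dosing (Treatment A) or before the breakfast that starts 30 minutes ahead of dosing (B, C and D). Section 7.3 rules out "Any nicotine product (including cigarettes) during confinement", but allows up to 10 cigarettes a day during washout.

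**The concern.** Section 9.4 names the 12-lead ECG as one of the measures by which safety and tolerability are judged. The only ECGs scheduled in a period are at 0, 4 and 6 h (plus the end-of-study tracing), so the 0-hour tracing is the natural reference for any change after dosing. If it was recorded at check-in, it differs from the 4-h and 6-h tracings in time of day, and possibly in food and nicotine state. A shift in heart rate or in an interval would then mix those differences with any effect of the drug.

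The window also allows the reference to vary within a subject: at check-in in one period and just before the dose in another. That adds noise to any comparison of changes between periods.

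In Period 1, Table 1, footnote 3, lets the screening ECG itself be done at check-in. Nothing in Table 6 stops one tracing from serving as both the eligibility ECG and the 0-hour ECG.

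**Working it through.** The plan gives no figure to reproduce here. The check is clock arithmetic on its own windows.

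**Inputs**
- Earliest 0-hour ECG: check-in, at least 10.5 h before the dose (Table 6; Table 1, footnote 5).
- Earliest 0-hour vital signs: 180 min = 3 h before the dose (Table 6).
- First post-dose reading: 4 h, with a window of 0.5 h either side for ECG and 20 min (0.33 h) for vital signs (Table 6, section 8.3).

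**Gap from reference to the 4-h reading**
- Check-in ECG, minimum confinement: 10.5 + 4 = 14.5 h. With the window: 14.5 - 0.5 = 14.0 h to 14.5 + 0.5 = 15.0 h. Longer confinement lengthens it.
- ECG recorded just before the dose: 4 - 0.5 = 3.5 h at the shortest.
- Vital signs, longest case: 3 + 4 = 7 h, or 3 + 4 + 0.33 = 7.33 h with the window.

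So in one subject the ECG gap can run from 3.5 h in one period to 15.0 h or more in another, all within Table 6.

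**Gap if the ECG had the vital-signs window**
- Longest case: 3 + 4 + 0.5 = 7.5 h.

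**Food state at check-in**
- Treatment A: the fast must start by 10 h before the dose. A check-in tracing at 10.5 h can precede it by 10.5 - 10 = 0.5 h even at minimum confinement.
- Treatments B, C and D: the fast must start by 10 + 0.5 = 10.5 h before the dose. A check-in tracing precedes it whenever admission is earlier than the minimum and the subject still eats that evening.

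**Nicotine state at check-in**
- The ban starts with confinement, so a light smoker may have smoked shortly before admission.

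**Passages side by side**
- Table 1, section 8.2 and section 8.3 all point to a Day 1 pre-dose ECG. Table 6 alone admits a Day -1 tracing under the same 0-hour label.

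**The case against.** The strongest reply is that check-in is not when the ECG is scheduled. Table 1 and section 8.3 put it on Day 1, section 8.2 does not list it at admission, and section 8 asks staff to work as close to nominal times as they can; Table 6 would then be only an outer limit. This is a fair account of the intention, but it leaves the gap open. A check-in tracing is inside the stated window and so is acceptable as written. The reply in fact shows that Table 6 is out of step with the rest of the schedule.

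A second reply stands, and limits the point. Each subject is scheduled for all four treatments, with ECGs at 4 and 6 h in every period and identical standardized meals. Treatments can be compared at those times without the 0-hour tracing. No change-from-baseline ECG analysis is specified, and section 9.4 plans no inferential safety analysis.

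A reader might infer more than the documents support:

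- **That Treatment A is worst served, because the first post-dose reading at 4 h comes after its peak.** Table 2 gives a fasting median Tmax of 2.77 h for intact tablets (4 - 2.77 = 1.23 h before the reading), but 5.00 h for dissolved tablets, which 4 and 6 h bracket. No Tmax is given for the suspension. Even on the intact-tablet figures, simple exponential decline leaves exp(-0.21 × 1.23) = 77% of peak at 4 h, and an illustrative one-compartment model gives about 93%. A subject peaking at 1 h would be lower, at about 53 to 62%, but that is not particular to the suspension.
- **That lunch spoils the 4-h readings.** Lunch at 4 h is only an example in section 6.6. Subjects fast for at least 4 h, the 4-h blood draw has a 1-minute tolerance, and coinciding readings should preferably come before the draw. Together these largely set the order.
- **That a reading is missing before 4 h.** The schedule is explicit: "Blood pressure and pulse rate will be measured before dosing (0-hour) and at 4 and 6 hours post-dose of each period". Nothing in the documents contradicts it. An extra reading would be a monitoring preference and an added procedure.
- **That the vital-signs reference is equally loose.** It is not; it has the 180-minute limit.

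**Conclusion.** The point holds for the 0-hour ECG window alone. As written, Table 6 accepts a Day -1 tracing taken 10.5 h or more before dosing, and so 14 h or more before the 4-h ECG, about twice the longest gap allowed for vital signs (14.5 / 7.33 = 2.0 at nominal ECG time). That conflicts with the Day 1 placement in Table 1 and section 8.3, and it gives a poor reference for post-dose ECG change.

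The consequence is minor. It is confined to descriptive ECG safety data, and the primary pharmacokinetic endpoints are unaffected. The conclusion assumes that the 0-hour ECG will be read as the reference for the 4-h and 6-h tracings, which the plan implies by its label but does not state. How often sites would use the early part of the window cannot be told from the documents. The secondary endpoints are redacted, so any role of the ECG among them cannot be judged.

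**What to change.** Reconcile Table 6 with Table 1 and section 8.3. In the pre-dose ECG row of Table 6, replace "From check-in to dosing" with the window already used for pre-dose vital signs, "Within 180 minutes prior to dosing". Add that in Treatments B, C and D the ECG is taken at the same point relative to breakfast in every period. If it is taken before the meal, 180 - 30 = 150 minutes remain available, since breakfast starts 30 minutes before the dose. A pre-breakfast tracing would still leave a meal effect in the change to 4 h in the fed periods; fixing the position makes that effect consistent across B, C and D but does not remove it.

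The change adds no procedure. It costs a tighter morning: up to 16 × 4 = 64 pre-dose ECGs must fit alongside the three pre-dose blood draws, the vital signs and, in the fed periods, breakfast.
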